Secondly, despite the benign nature of the disorder, self-advised medications by caregivers and misdiagnosis by physicians in developing countries, where childhood diarrhea remains a major public health problem, may lead to unnecessary laboratory investigations and misapplication of drugs, especially antibiotics. Anecdotal evidence suggests that toddlers' diarrhea is wrongly managed as one of the infective diarrheas by physicians leading to huge treatment costs, and the promotion of antibiotic resistance.

As a novel alternative treatment option, ranitidine given orally for a short duration of 10 days will not only ensure prompt resolution of diarrhea but also ensure better compliance by caregivers. In addition, the treatment cost will be more affordable while the side effects for children at this phase of life are very minimal or non-existent.

Study goals and objectives

Study goal: To establish an alternative therapeutic strategy for toddlers' diarrhea using pharmacotherapy

Primary objective: To determine the effectiveness of a short course of daily oral ranitidine in the treatment of toddlers' diarrhea.

Secondary objective: To compare the effectiveness of oral ranitidine with the probiotic (*Lactobacillus rhamnosus*) in the treatment of toddlers' diarrhea

Study design

A parallel-group randomized controlled trial (RCT)

Methodology

Setting: Pediatric Out-patient Clinic at the University of Nigeria Teaching Hospital (UNTH), Ituku-Ozalla Enugu; and Restoration Medical Centre (Children's Clinic), [name]

Participants' recruitment: Sequential enrolment of 40 participants who met the following eligibility criteria:

(i) Age range of 1-3 years (ii) Duration of diarrhea lasting 3 weeks or more (iii) Historical evidence of the characteristic stooling pattern (iv) Absence of pyrexia and signs of dehydration (v) Normal anthropometry and (vi) Normal findings on stool analysis, microscopy and culture.

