Study design: The design is a parallel-group randomized controlled trial (RCT) in which each participant is to be randomly assigned to three groups after meeting the eligibility criteria. For the randomization procedure, we will use permuted-block randomization. The three groups of subjects will consist of a group to be given daily oral ranitidine (3mg/kg) for 10 days (oral ranitidine group-ORG), the group that will receive probiotic for 10 days (PBG) and the control group that will be given a placebo (vitamin C- 50mg daily) for the same duration.

Twenty participants will be assigned to each group- ORG, PBG, and PG. A proforma will be used to record the bio-data, anthropometry of participants, and findings of their stool analysis and stool microscopy/culture.

Intervention: In the ORG- participants will be given oral ranitidine (3mg/kg/day) once daily for 10 days; in the PBG, they will receive probiotics in appropriate doses for 10 days; while in the PG,

the participants will be given vitamin C (50 mg) daily for the same duration. We will ensure allocation concealment by using sequentially numbered, opaque, sealed envelopes (SNOSE) containing the medications. In a double-blind fashion, each enrolled participant will be given color-coded envelopes containing ranitidine, the probiotic, or vitamin C tablets unknown to both the caregivers and outcome assessors.

Follow-up/outcome measures: Stool frequency and consistency will be recorded on days 5 and 10. Any adverse drug reactions will be noted on these follow-up days. There will also be follow-up documentation of stool frequency and consistency 30 days after the end of interventions. Failure of participants to present for documentation of the study outcomes on any of the days will be the qualification for dropping out.

Safety considerations: Follow-up on adverse drug reactions (especially adverse reactions related to ranitidine) will be extended up to 60 days after the end of the intervention. Clinical monitoring of participants for adverse reactions to probiotics will be ensured. Provision will be made for hospitalization and appropriate intervention

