Data management and statistical analysis: Data entry and analysis will be done using the Statistical Package for Social Sciences (SPSS) version 25 for Windows. Data will be scrutinized for incorrect information and will be cleaned periodically. The Student's t-test will be used to determine any statistically significant differences in the mean daily stool frequencies of the three intervention groups on the follow-up days. ORG and PBG will be used to report the study effect size. Two standardized measures (Cohen's d and estimation of risk difference) will be used. A 95% confidence interval will be assumed while a p -value < 0.05 will be adopted as the level of statistical significance.

For sample size determination, a predetermined table with the desired statistical power of 0.95 and a Cohen's d (effect size) value of 0.8 will be used, approximating a sample size of 42 (To give room for attrition, 40 will be the final sample size). The value of 0.8 will be chosen to correspond to a large effect size in the predetermined table, indicating the likelihood of a stronger effect.

Study expected outcomes: Normalization of stool frequency and consistency will be the expected outcome of the intervention with oral ranitidine. If no adverse reactions are recorded during and after the study, the intervention may become a paradigm shift in the treatment of toddlers' diarrhea. Clinicians may be more inclined to use this novel pharmacologic approach than the conventional non-pharmacologic methods.

Publication policy/target: We aim to disseminate the findings by publishing them in a reputable international journal within a year of completing the study. [name] will take the lead in the publication. All the investigators will be co-authors.

Duration of research: A proposed period of three years will be allocated for the project implementation and publication of findings. The proposed details include monthly enrollment of eligible participants for 6 months, allocation of participants to intervention groups within a month, follow-up of participants and weekly documentation of outcomes for 6 months, and data analysis for 12 months/manuscript drafting for publication for another 12 months.

Anticipated problems: Seamless participants' enrollment may be affected in the government-run tertiary hospital setting chosen as the study site because of clientele attendance and administrative

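### A two-group t-test is applied to three groups on three days at an unadjusted 0.05, and the protocol does not say which contrast and day decide effectiveness

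*Protocol*

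**What the plan says.** The analysis is set out in the protocol under Data management and statistical analysis: "The Student's t-test will be used to determine any statistically significant differences in the mean daily stool frequencies of the three intervention groups", at each follow-up. The threshold follows: a p-"value < 0.05 will be adopted as the level of statistical significance". No overall three-group test, adjustment or order of testing is given.

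The follow-up days come from Follow-up/outcome measures: "Stool frequency and consistency will be recorded on days 5 and 10", and there is also "follow-up documentation of stool frequency and consistency 30 days after the end of interventions". That makes three assessments.

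The objectives are:
- "Primary objective: To determine the effectiveness of a short course of daily oral ranitidine in the treatment of toddlers' diarrhea". No comparator or day is named.
- "Secondary objective: To compare the effectiveness of oral ranitidine with the probiotic".

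The Study design text calls the vitamin C arm the control group. The analysis section, however, says that the study effect size is to be reported from ORG and PBG, which is the contrast of the secondary objective.

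**The concern.** Student's t-test cannot compare three means at once. Applied to three groups it has to become a set of pairwise tests, repeated on each day. With every test at 0.05 and no contrast or day singled out, 0.05 is the error rate of each test and not of the conclusion that ranitidine works.

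The protocol also points two ways on the main contrast: the objectives lean towards ORG vs PG, while the effect-size sentence uses ORG vs PBG. An analyst could follow the plan faithfully and still choose, after seeing the data, which pair and which day to present as the result. A choice made at that stage cannot be undone by later adjustment. The protocol foresees that the result could change how the condition is treated, so the rule behind a positive claim needs to be fixed beforehand.

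**Working it through.** **Inputs from the protocol**
- Three groups, hence 3 × 2 / 2 = 3 pairs: ORG vs PG, ORG vs PBG, PBG vs PG.
- Three assessments: day 5, day 10 and 30 days after the end of interventions.
- Threshold 0.05 per test. Sidedness is not stated; two-sided is assumed, in keeping with the 95% confidence interval.
- Group size: Study design says "Twenty participants will be assigned to each group- ORG, PBG, and PG", whereas Participants' recruitment says "Sequential enrolment of 40 participants who met the following eligibility criteria", about 40 / 3 ≈ 13 per group. Both sizes were run.

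**Inputs that the protocol does not give**
- The correlation of stool frequency between days within a child. It is varied, with 0 to 0.7 as the main range and higher values shown as well.
- Which pairs are tested, and whether one significant day is enough. Each reading is shown separately.

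The protocol states no overall error rate, so there is no figure of its own to reproduce.

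**Step 1: number of tests of stool frequency**
- ORG vs PG only: 1 × 3 = 3
- Both ranitidine contrasts: 2 × 3 = 6
- All pairs: 3 × 3 = 9

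**Step 2: reference if the tests were independent**, 1 − 0.95^k
- k = 3: 14.3%
- k = 6: 26.5%
- k = 9: 37.0%

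The last two are too high, because pairwise contrasts share groups. Correlation between days lowers all three.

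**Step 3: simulation with no true difference.** Normal data, pooled two-sample t-tests, the same correlation between any two days, 60,000 runs per cell. The entries are the chance of at least one p below 0.05 with 20 per group.

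| Correlation between days | ORG vs PG, 3 tests | Both ranitidine contrasts, 6 tests | All pairs, 9 tests |
|---|---|---|---|
| 0 | 14.2% | 24.9% | 32.6% |
| 0.5 | 12.3% | 22.2% | 28.6% |
| 0.7 | 11.2% | 19.4% | 25.0% |
| 0.9 | 8.5% | 14.8% | 19.5% |
| 0.99 | 6.1% | 11.0% | 14.4% |

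With 13 per group the figures are almost the same (for nine tests, 32.3% at correlation 0 and 25.5% at 0.7), so the conflict over group size does not affect this point. All three pairs on a single day give about 12%.

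**Step 4: what pre-naming does.** One contrast on one day has a 5% error. Suppose ORG vs PBG is tested on that day only after a significant ORG vs PG. If ORG and PG truly do not differ, any false claim first needs that 5% error. If they do differ, the only possible false claim is the second test, again at 5%. The pair is therefore held at 5% without splitting the level.

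**The case against.** **The protocol states no rule that one significant day is enough.** This is correct. Asking whether there are any significant differences is ordinary wording, and the Project Summary expects normalization on the selected days, which could mean all of them. Requiring ORG vs PG to be significant on all three days would give an error below 1% at correlations up to 0.7. But the protocol does not fix that rule either. The fault is a missing decision rule, and the inflation is conditional on how the gap is filled.

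**The objectives already rank the contrasts.** Largely so. Ranitidine's effectiveness comes first, ranitidine vs probiotic second, and vitamin C is the control. A reader might infer that the trial has no primary comparison at all; that goes too far. What unsettles the implied ranking is the effect-size sentence, and nothing in the protocol settles the day.

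**The nine-test figure overstates the harm.** A reader might take 25-32% as the chance of wrongly declaring ranitidine effective. It is not: three of the nine tests are PBG vs PG, which no objective asks about and which cannot support a claim for ranitidine. The range also depends on a correlation no higher than 0.7. For ORG vs PG in the direction favouring ranitidine, any-day testing gives about 5.4-7.3% over correlations 0.7 to 0, against a nominal 2.5%. That is 5.4 / 2.5 ≈ 2.2 to 7.3 / 2.5 ≈ 2.9 times the nominal rate, so real inflation remains.

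**Multiplicity belongs in a statistical analysis plan.** Often it does, and its absence alone would not be a finding. Here the protocol itself prescribes a two-group test for three groups at an unadjusted level and an effect size from the secondary contrast.

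**Conclusion.** The point holds as a gap in the decision rule: a two-group test is set for three groups on three days at an unadjusted 0.05, the deciding contrast and day are not stated, and the effect-size sentence conflicts with the contrast that the primary objective implies.

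If significance on any day were taken as success, the chance of at least one false positive would be:
- about 11-14% for ORG vs PG, the most relevant figure (about 8% at correlation 0.9);
- 19-25% for the two ranitidine contrasts;
- 25-32% for all nine tests (about 20% at correlation 0.9).

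The ranges assume two-sided tests, approximately normal data and a within-child correlation of 0.7 down to 0, none of which the protocol states. They cover stool frequency only; testing consistency in the same way would raise them. Any reading in which one significant result out of several suffices exceeds 5%.

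**What to change.** In the data management and statistical analysis section:

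1. Name ORG vs PG on stool frequency, on one pre-specified day, as the single confirmatory test at two-sided 0.05. Day 10, the end of the course, is an example. Another day controls the error equally well if it is fixed in advance.
2. Test ORG vs PBG on the same day, at 0.05, only if the first test is significant.
3. Report the other days, PBG vs PG and stool consistency as estimates with 95% confidence intervals, without claims of significance.
4. Reword the effect-size sentence so that the primary effect size is ORG vs PG and ORG vs PBG is secondary.
5. Optionally, take both contrasts from one three-arm model, so that all groups contribute to the error variance. Pre-specified pairwise t-tests in the same order control the error just as well.

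The cost is a few sentences, with no extra participants or visits. The downside is that the other days become descriptive, so an effect seen only on one of them could not be claimed as confirmed.

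### The claimed power of 0.95 at d = 0.8 needs 42 children in each group; the enrolment the protocol states gives about 0.50 (40 in all) or 0.69 (20 per arm)

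*Protocol*

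**What the plan says.** The sample size paragraph of the Protocol (Data management and statistical analysis) names a "desired statistical power of 0.95 and a Cohen's d (effect size) value of 0.8", looked up in a predetermined table, and continues: "approximating a sample size of 42 (To give room for attrition, 40 will be the final sample size". It does not say whether 42 is per group or in total, and it gives no attrition rate.

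The same section fixes the analysis: "The Student's t-test will be used to determine any statistically significant differences in the mean daily stool frequencies of the three intervention groups", with "p -value < 0.05 will be adopted as the level of statistical significance". Whether the test is one- or two-sided is not stated.

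Two statements in the Methodology determine how many children enter each comparison:

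- Participants' recruitment: "Sequential enrolment of 40 participants who met the following eligibility criteria". The Project Summary also gives 40, and both places describe a single trial with three randomised groups.
- Study design: "Twenty participants will be assigned to each group- ORG, PBG, and PG". That makes 3 × 20 = 60 children.

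**The concern.** Standard tables for comparing two means, indexed by power and Cohen's d, give the number per group. If 42 is such an entry, a three-arm trial with 40 children in all has about a third of the required number in each arm, and 20 per arm is less than half of it. Reducing the figure to make room for losses also goes in the wrong direction.

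The power statement is the protocol's only justification for its size. It tells an ethics committee, and later the readers of the result, that a large ranitidine effect would be missed only 5 times in 100. If the true figure is several times higher, a non-significant result on the primary objective could be given more weight against ranitidine than the data can bear.

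**Working it through.** **Inputs, all from Data management and statistical analysis unless noted**

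- Power 0.95; d = 0.8 (difference in means divided by the SD); significance level 0.05; Student's t-test between two groups.
- Group sizes: 40 over three arms (Project Summary; Participants' recruitment), which is 14 + 13 + 13; or 20 per arm (Study design).
- Assumption: the test is two-sided. The protocol does not say, but this is the reading that reproduces 42.

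**Step 1. Reproduce the 42.** The normal approximation for each group is

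n = 2 (z₀.₉₇₅ + z₀.₉₅)² / d² = 2 × (1.960 + 1.645)² / 0.64 = 40.6, so 41.

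The exact calculation with the noncentral t distribution gives 41.59, so **42 per group**. Power is 0.947 at 41 per group and 0.952 at 42. The protocol's number is reproduced as a per-group size.

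**Step 2. Can 42 be a total?** The variants tried were:

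| Reading | Result |
|---|---|
| Two-sample t-test, one-sided | 34.5, so 35 per group |
| Paired or one-sample t-test | 22.3, so 23 |
| Two-sample t-test at 0.05/3 | 52.4, so 53 per group |
| Three-group ANOVA, f = 0.4 | about 100 in total |
| Three-group ANOVA, means spanning d = 0.8 | 112 to 148 in total |
| Three-group ANOVA, f = 0.8 | 28 in total |
| 42 as a two-group total (21 v 21) | power only 0.716 |

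None gives 42 as a total at power 0.95.

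**Step 3. Power at the stated enrolment.** With group sizes n₁ and n₂, the noncentrality is δ = d √(n₁n₂/(n₁+n₂)) on n₁+n₂−2 degrees of freedom. Power is the probability that |t| exceeds its two-sided 5% critical value. For 20 v 20: δ = 0.8 × √10 = 2.530, 38 degrees of freedom, critical value 2.024, power 0.693.

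| Groups compared | Power, two-sided | Power, one-sided | d detectable with power 0.95 (two-sided) |
|---|---|---|---|
| 42 v 42 | 0.952 | 0.977 | 0.80 |
| 20 v 20 (60 in all) | 0.693 | 0.799 | 1.17 |
| 14 v 13 (40 in all) | 0.515 | 0.646 | 1.45 |
| 13 v 13 (40 in all) | 0.499 | 0.632 | 1.47 |

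The chance of missing d = 0.8 is 1 − 0.693 = 0.31 at 20 per arm and 1 − 0.499 = 0.50 at 13 per arm. A one-sided test does not restore 0.95 in either case.

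**Step 4. Attrition.** An allowance divides the required number by the expected retention. The protocol gives no rate, so the following rates are assumptions for illustration. At 10% loss, 42 / 0.90 = 46.7, so 47 would be enrolled per group. Conversely, a loss of about 15% from the stated sizes leaves 17 per arm (power 0.62) or 11 per arm (power 0.43).

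**The case against.** The protocol never says that 42 is a total and never divides it by three. Its only explicit allocation is 20 per arm. The authors may have taken 42, lowered it to 40, as the total for a two-group comparison, arrived at 20 per group, and then added a third arm of 20. On that account the relevant power is 0.69, and leading with 0.50 shows the worst case. The protocol also plans a 95% confidence interval and Cohen's d, which would show the imprecision of a null result. Finally, the primary objective names no comparator, so quoting power for ranitidine against placebo is the reviewer's choice.

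Much of this is fair, but it does not save the 0.95. How the authors reached 40 is a matter of inference, and whether 0.50 or 0.69 applies depends on a contradiction (40 enrolled against 3 × 20 = 60) that the protocol must settle. Still, the final sample size of 40 is the same 40 that two other places enrol for all three groups, so reading it as the trial total is reasonable. Reading 40 as a per-group number would give 0.94, but neither enrolment statement allows it. The choice of contrast makes no difference to power when the arms are equal. A reported confidence interval would soften a misreading of a null result, but would not make the power statement true.

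**Conclusion.** The concern holds. The figure of 42 is correct for these inputs only as the size of each compared group. Under the enrolment the protocol states, power at d = 0.8 is about 0.50 (40 children over three arms) or 0.69 (20 per arm), a shortfall of roughly 26 to 45 percentage points from 0.95. The effect detectable with power 0.95 is d = 1.17 or about 1.45 to 1.47, well above the 0.8 that the protocol already calls large. The reduction from 42 to 40 is not an allowance for attrition.

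These figures assume a two-sided 5% test of one pair of arms with no multiplicity adjustment and no dropout. The one-sided alternative gives about 0.63 to 0.65 or 0.80, so the conclusion does not depend on sidedness. Dropout would lower every figure. The power statement must be corrected.

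**What to change.** In the sample size paragraph of Data management and statistical analysis:

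1. State that 42 is the number needed in each of two groups for a two-sided 5% t-test at d = 0.8 and power 0.95.
2. Reconcile the 40 in the Project Summary and Participants' recruitment with the 20 per arm in Study design, and use one figure throughout.
3. Replace 0.95 with the power that figure gives for ranitidine against placebo at d = 0.8 (about 0.69 at 20 per arm, about 0.50 at 13 to 14 per arm), or give the detectable d instead.
4. Delete the statement that going from 42 to 40 makes room for attrition. State the expected loss and quote power for the number expected to be evaluable.

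This costs protocol wording only and needs no additional recruitment, though the stated power becomes less favourable. Keeping 0.95 as a real target would need 42 evaluable children per arm, 3 × 42 = 126 in all before any attrition allowance; that choice belongs to the investigators.

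### A zero count of adverse reactions in a ranitidine arm of 13 to 20 children cannot support the change of practice that the protocol ties to it

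*Protocol*

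**What the plan says.** The Study expected outcomes paragraph first names normal stools as the result expected from ranitidine. It continues: "If no adverse reactions are recorded during and after the study, the intervention may become a paradigm shift". The sentence after that suggests that clinicians may then come to favour the drug over non-drug management.

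The background text ahead of Study goals and objectives already expects little harm. It says that "the side effects for children at this phase of life are very minimal or non-existent".

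Collection of safety data is planned. Under Follow-up/outcome measures, reactions are noted on days 5 and 10. Under Safety considerations, follow-up for reactions runs to 60 days after treatment ends.

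The size of the ranitidine arm is stated in two ways. The Study design paragraph under Methodology says: "Twenty participants will be assigned to each group- ORG, PBG, and PG". Participants' recruitment says: "Sequential enrolment of 40 participants who met the following eligibility criteria". These 40 are to be divided among three groups.

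**The concern.** The sentence goes from a count of zero to a possible change of practice and says nothing about how little a zero means in an arm this small. Zero observed reactions does not mean a zero reaction rate, and the smaller the arm, the easier a zero is to obtain. The background text already expects almost no side effects, so a zero would readily be read as confirmation.

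What is at stake is the conclusion. A report that followed this sentence could present ranitidine as safe enough in toddlers to displace non-drug management, on data that leave a substantial reaction rate open.

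**Working it through.** **The plan's own figures.** The protocol states no figure for safety precision. Its one sample-size figure, 42 (Cohen's d of 0.8, power 0.95), concerns efficacy. It reproduces as 42 per group for a two-group, two-sided t-test at 0.05, and it says nothing about reaction rates.

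**Inputs.**
- Events in the ranitidine arm: 0, as the sentence supposes.
- Arm size n: 20 as stated under Study design, or 40/3 = 13.3, that is 13 or 14, from the total of 40. Roughly equal allocation is assumed.
- Confidence level: 95%, from Data management and statistical analysis ("A 95% confidence interval will be assumed while a p -value < 0.05 will be adopted as the level of statistical significance"). Sidedness is not stated, so both conventions are shown.

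**Step 1: upper limit for the reaction rate after 0 events in n.** The exact (Clopper-Pearson) limit is 1 − 0.025^(1/n) two-sided and 1 − 0.05^(1/n) one-sided.

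| n | Two-sided 95% | One-sided 95% |
|---|---|---|
| 20 | 1 − 0.025^(1/20) = 16.8% | 1 − 0.05^(1/20) = 13.9% |
| 14 | 1 − 0.025^(1/14) = 23.2% | 1 − 0.05^(1/14) = 19.3% |
| 13 | 1 − 0.025^(1/13) = 24.7% | 1 − 0.05^(1/13) = 20.6% |

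The two-sided limits run from about 1 in 6 to about 1 in 4, and the one-sided limits from about 1 in 7 to about 1 in 5. Losses widen them: with 10 children followed, the two-sided limit is 1 − 0.025^(1/10) = 30.8%.

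**Step 2: chance of no reaction in the ranitidine arm at a true rate p.** This is (1 − p)^n. The protocol gives no rate, so those below are assumptions chosen to show a range.

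| Assumed p | n = 20 | n = 13 |
|---|---|---|
| 1% | 0.99^20 = 0.82 | 0.99^13 = 0.88 |
| 5% | 0.95^20 = 0.36 | 0.95^13 = 0.51 |
| 10% | 0.90^20 = 0.12 | 0.90^13 = 0.25 |

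A zero is the usual result at 1%, quite possible at 5%, and uncommon at 10%.

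**The case against.** Four points on the other side have force.

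1. **It is not an analysis rule.** The sentence stands apart from the statistical section and speaks only of what may follow, and no test or stopping step depends on it. It also comes after the efficacy expectation, so zero reactions is not offered as sufficient on its own. A reader might infer a formal safety criterion that decides the trial's conclusion, but the text does not set one. This lowers the weight of the point. It does not remove it, because the step from a zero count to a change of practice is still stated, without any caveat about precision.

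2. **Prior safety evidence is invoked.** The background says that ranitidine is licensed in children for peptic ulcers and appeals to its paediatric safety profile. It would therefore be wrong to infer that the investigators rest safety on this trial alone. Whether that evidence suffices cannot be judged from the protocol. The sentence at issue, however, names this study's own record as the condition.

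3. **Intervals and comparisons between arms belong in a statistical analysis plan.** That is right, and their absence from the protocol is not a fault. The fault is the inference that the protocol does state, which a separate analysis plan would leave in place.

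4. **The condition may cover all arms.** The sentence does not confine the reactions to ranitidine. If every arm had a 5% rate, no reaction anywhere would have probability 0.95^40 = 0.13 or 0.95^60 = 0.05, well below the figures for one arm. The ranitidine arm nevertheless remains the right denominator for a limit on the rate under ranitidine, so Step 1 is unaffected.

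A reader might also infer that a zero is likely even when reactions are frequent. The figures do not show that: at an assumed 10% the probability is 0.12 or 0.25, and at 5% it only just passes one half, and only in the smaller arm.

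**Conclusion.** The point holds as a minor one, between an optional and a recommended change. Zero reactions in the ranitidine arm would leave rates up to 16.8% (n = 20) or 24.7% (n = 13) compatible with the data by the two-sided exact 95% limit, or 13.9% and 20.6% one-sided. A zero count therefore cannot carry the inference that the protocol attaches to it. No test or efficacy result is affected; what changes is what the trial may conclude about safety.

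The limits assume that every child in the arm is followed for reactions. The spread between 13 and 20 comes only from the protocol's two statements of size. The probabilities in Step 2 illustrate the point at assumed rates and are not predictions.

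**What to change.** In Study expected outcomes, delete the link from zero recorded reactions to a change of practice. Say instead that:

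- adverse reactions will be reported by arm with exact 95% confidence limits;
- a zero count in the ranitidine arm will be given with its upper limit, calculated for the number of children actually followed (about 17% with 20 children, two-sided);
- this trial alone cannot establish safety.

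The change rewrites one paragraph and adds a few lines of analysis on data already to be collected. It needs no further participants or visits. Its cost is a more modest claim.

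The conflict between 40 in total and 20 in each of three groups has to be reconciled separately. Until it is, the size of the limit cannot be stated in advance.
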